6.9.2. Prohibited concurrent medications

The following drugs are prohibited during the course of the study.

- Tumor necrosis factor [TNF] inhibitors, vedolizumab or others biologic therapies with a wash-out period of at least 8 Weeks prior to the screening visit;
- JAK inhibitors with a wash-out period of at least 4 Weeks prior to the screening visit;
- Topical corticosteroids and topical 5-aminosalicylic acid preparations with a wash-out period of at least 2 Weeks prior to the screening visit;
- Cyclosporine and tacrolimus with a wash-out period of at least 4 Weeks prior to the screening visit;
- Vaccination with live components during the study and up to 8 Weeks after the last dosing;
- Drugs that could interact with ABX464 should be avoided especially the CYP1A2 substrates (cf. Appendix #1). The following CYP1A2 substrates with a narrow therapeutic margin are prohibited during the whole course of the study (Clozapine, theophylline, ropinirol, warfarin and methadone). In case of concomitant treatment with ondansetron the maximal daily dose must be limited to 8 mg;
- Drugs that inhibit or induce CYP1A2 (cf. Appendix #1).
- Drugs that inhibit UGT1A9 activity and inhibitors of OATP1B1/1B3 transporters (cf. Appendix #1).
- Use of any investigational or non-registered product within 3 months or within 5 half-lives preceding baseline, whichever is longer and during the study.

7. PATIENT COMPLETION AND WITHDRAWAL

7.1. Patient Completion

Treatment with ABX464/Placebo shall continue until Day 113, except if a patient fulfils a premature discontinuation criterion (defined below). After Day 113, patients who are willing to carry on the study treatment will be able to take part in the long-term maintenance study (ABX464-104).

In any other case, patients will exit the study (EoS) and will be treated according to the standard of care. The ABX464-104 follow-up study is a separate clinical protocol subject to health authorities and ethics committee approvals.

7.2. Premature trial discontinuation

A patient can be withdrawn at any time from the study for the following reasons:

- Investigator's decision; patient that would experience a treatment failure during the study may be withdrawn at any time. S/he will have to be treated according to standard of care as soon as s/he is off from study treatment;
- An Adverse Event or an intercurrent condition that preclude continuation of treatment;
 - Specifically, an increase $\geq 3.0 \times$ ULN in liver transaminases (AST/SGOT and/or ALT/SGPT) or an increase $\geq 2.0 \times$ ULN in Alkaline phosphatase or in total bilirubin requires close observation with repeating liver enzymes and serum bilirubin tests two times weekly and clinical investigation to understand the etiology of this elevation. Frequency of retesting can decrease to once a month if the abnormality stabilizes after this initial two weeks of follow-up and if the patient is asymptomatic. Discontinuation of the study treatment should occur if:
 - ALT or AST $> 8 \times$ ULN
 - ALT or AST $> 5 \times$ ULN for more than 2 weeks
 - ALT or AST $> 3 \times$ ULN and total bilirubin $> 2 \times$ ULN or INR > 1.5
 - ALT or AST $> 3 \times$ ULN with appearance of fatigue, nausea, vomiting, right upper quadrant pain or tenderness, fever, rash, and/or eosinophilia ($> 5\%$).
- Worsening of the UC defined, from Week 8 onwards, as a 2-point increase in the pMMS, with pMMS ≥ 4 on 2 separate occasions 7 day-apart and confirmed by an endoscopy sub-score of 2 points or higher;
- Major protocol violation;
- Patient's decision;
- Withdrawal of consent;

A patient who prematurely exits the study will not be replaced.

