From Week 8 onwards, in the event of clinical progression of the disease defined as at least a 2-point increase from the screening in partial Modified Mayo Score (pMMS) with a Modified Mayo Score ≥ 4 confirmed by an endoscopy sub score of 2 points or higher, the patient will exit definitively the study.

Approximately 244 patients will be randomized in this study (i.e. 61 patients per study treatment arm).

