5.3.6. Modified Mayo Score - Stool and Rectal Bleeding Frequency

The Stool and Rectal Bleeding frequency assessment will be based on the Mayo scoring system which is the most commonly used index in clinical trials.

Total Mayo score consists of 4 items: stool frequency, rectal bleeding, flexible sigmoidoscopic examination, and a physician global assessment (Appendix #3). Modified Mayo Score (MMS) consists of 3 items (stool frequency, rectal bleeding, flexible sigmoidoscopic examination).

Partial Modified Mayo Score (pMMS) consists of only 2 items (stool frequency, rectal bleeding).

Although the physician global assessment is performed as part of the patient care, only the pMMS and MMS will be assessed as endpoints according to regulatory guidance. Stool frequency and rectal bleeding frequency will be recorded from the patient e-Diary at each patient visit by the Investigator.

Attention: Investigators should train his/her patient how to record stool frequency and rectal bleedings in the e-Diary. Instruction booklet, detailing the FDA requirements for Patient Reported Outcomes, will be provided to patients and investigators.

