Flexible sigmoidoscopy with rectal and/or sigmoidal biopsies will be performed at screening, at Day 57 +/- 4 days (Week 8) and at Day 113 +/- 4 days (Week 16). The Day 113 measurement will only be taken if the patient does not experience endoscopic improvement (i.e. endoscopy sub-score of 2 or 3) at Day 57. In the event of clinical progression of the disease after Week 8, defined as at least a 2-point increase from screening in pMMS, with a MMS ≥ 4 confirmed by an endoscopy sub score of 2 points or higher, the patient will exit the study.

Study Design

Document: \\ieedc-vnasc01\BIOSdata\Abivax\ABX464\FZA92720\Biostatistics\Documentation\SAP\ABX464-103_SAP_V2.0_10MAY2021

Author: [REDACTED]

Version Number: 2.0
Version Date: 10May2021

Template No.: CS_TP_BS016 Revision 5

Reference: CS_WI_BS005

Effective Date: 01Apr2018

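### The protocol gives two inconsistent exit rules for disease worsening, and the one in its design section cannot be met by patients who enter with a pMMS of 5 or 6

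*Protocol*

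**What the plan says.** **Design rule.** The synopsis (Study Design and Methodology) and Protocol 3.1.1 define clinical progression, from Week 8 onwards, as "at least a 2-point increase from the screening in partial Modified Mayo Score (pMMS) with a Modified Mayo Score ≥ 4". The sentence ends: "confirmed by an endoscopy sub score of 2 points or higher, the patient will exit definitively the study". SAP 3.1 has the same criteria, "defined as at least a 2-point increase from screening in pMMS, with a MMS ≥ 4 confirmed by" endoscopy, and also has the patient leave, but it places the rule after Week 8. None of the three texts mentions a repeat assessment.

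**Discontinuation rule.** The synopsis (Premature trial discontinuation) and Protocol 7.2 define worsening, from Week 8 onwards, "as a 2-point increase in the pMMS, with pMMS ≥ 4 on 2 separate occasions 7 day-apart", with endoscopic confirmation at the same level. Neither says which visit the rise is measured from. The list in 7.2 opens with "A patient can be withdrawn at any time from the study for the following reasons". Section 7.1, however, has treatment run to Day 113 "except if a patient fulfils a premature discontinuation criterion (defined below"), which points to the 7.2 list.

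**Scale.** Protocol 5.3.6 states: "Partial Modified Mayo Score (pMMS) consists of only 2 items (stool frequency, rectal bleeding"). Appendix 3 scores each item from 0 to 3.

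**The concern.** Both rules are in force in the same protocol, and the synopsis contains both. They share the endoscopic condition but differ in reference visit, score threshold, number of occasions and stated force, and nothing ranks one above the other. Two sites with the same patient could act at different times, each with a section of the protocol behind it.

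The rule exists to protect patients, and it also shapes the later data. A patient who leaves before Day 113 has no Week 16 visit and misses the point at which roll-over to the extension study is offered. SAP 15.2.1.1 bases the Week 16 remission percentage on patients in the arm at Week 16, and the component imputation in SAP 7.3 is written for Week 8. The exit rule therefore helps decide who is counted at Week 16.

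A second problem is the bounded scale. A rise of 2 from screening needs room above the screening score, and patients who enter near the top of the pMMS have none.

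**Working it through.** **1. The two rules side by side**

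| Element | Synopsis design text, Protocol 3.1.1, SAP 3.1 | Synopsis discontinuation list, Protocol 7.2 |
|---|---|---|
| Reference for the rise | Screening | Not stated |
| Score threshold | MMS ≥ 4 | pMMS ≥ 4 |
| Occasions | No repeat mentioned | Two, a week apart |
| Endoscopy sub-score | ≥ 2 | ≥ 2 |
| Start | From Week 8 (protocol); after Week 8 (SAP) | From Week 8 |
| Force | Patient leaves | Permissive opening in 7.2; 7.1 treats the criteria as ending treatment |

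I read the rise in 7.2 as 2 points or more.

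**2. A patient on whom they disagree.** Take a constructed case with screening pMMS 3 and endoscopy 3, so MMS 6. At Day 57 the pMMS is 5 and endoscopy 2, so MMS = 5 + 2 = 7. The rise is 5 − 3 = 2.
- Protocol 3.1.1: met, and the patient leaves.
- SAP 3.1: unclear, because Day 57 is Week 8 and the SAP says after Week 8.
- Protocol 7.2: not yet met, because there has been one occasion only. If pMMS is 3 a week later, it is not met at all, and 7.1 has treatment continue.

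The flow chart in Protocol 5.1 schedules no on-treatment visit one week after Day 57, 85 or 113.

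**3. The ceiling.** Inputs: pMMS is the sum of two 0–3 items, so 0 to 6. MMS is the sum of three 0–3 items, so 0 to 9 (SAP 15.1.1 states the same range). Entry requires MMS 5–9 and endoscopy 2 or 3 (Protocol 4.2.1). Then screening pMMS = MMS − endoscopy, and the largest possible rise = 6 − screening pMMS.

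| Screening MMS | pMMS (largest rise), endoscopy 2 | pMMS (largest rise), endoscopy 3 |
|---|---|---|
| 5 | 3 (3) | 2 (4) |
| 6 | 4 (2) | 3 (3) |
| 7 | 5 (1) | 4 (2) |
| 8 | 6 (0) | 5 (1) |
| 9 | not possible | 6 (0) |

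A rise of 2 from screening is impossible at pMMS 5 or 6: all of MMS 8 and 9, and MMS 7 with endoscopy 2. As a check, all 64 sub-score combinations were enumerated. With screening as reference, and before any repeat requirement, the number of later states that meet the criteria is 12, 6, 2, 0 and 0 for screening pMMS 2, 3, 4, 5 and 6. The counts are the same for both rules.

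**4. The score thresholds.** The lowest screening pMMS for entry at MMS 5–9 is 2. After a rise of 2 from screening, pMMS is at least 4, and with endoscopy ≥ 2 the MMS is at least 4 + 2 = 6. MMS ≥ 4 therefore never binds, and neither does pMMS ≥ 4 when measured from screening. SAP 5.2.4 allows a baseline MMS of 4 under the original protocol. With endoscopy 3 such a patient has pMMS 1, and the smallest MMS at trigger is 3 + 2 = 5, so MMS ≥ 4 still does not bind. Only here do the thresholds separate the rules: a rise to pMMS 3 satisfies MMS ≥ 4 but not pMMS ≥ 4.

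**5. If 7.2 has another reference.** SAP 15.2.1.7 uses Day 1 as baseline pMMS, although for analysis and not for exit. With a Day 1 reference the ceiling applies to Day 1 pMMS 5 or 6 instead. With an on-study reference it can disappear: screening 6, later 3, then 5 on two occasions is a rise of 2 with pMMS ≥ 4.

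**The case against.** The best defence is that the conflict is smaller than it looks, and much of that stands.

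- **A reader might infer that sites cannot follow both rules.** That is too strong. With screening as reference, every patient who meets 7.2 also meets 3.1.1, so a site that acts on 3.1.1 breaches neither. What remains is that the week-apart confirmation in 7.2 then has no effect.
- **A reader might infer that the patients with the worst symptoms can meet neither rule.** This is shown for 3.1.1. For 7.2 it holds only if the unstated reference is screening (step 5).
- **A reader might infer that these patients have no way out.** Section 7.2 lets the investigator withdraw a patient for treatment failure at any time, with no score threshold. That route is discretionary, so it does not resolve the inconsistency.
- **The contrast between mandatory and discretionary exit is weak.** Section 7.1 makes the 7.2 criteria end treatment. The permissive opening of 7.2 also covers withdrawal of consent and liver criteria that are themselves worded as stopping rules.
- **The difference in score is nearly nominal.** If both rules are measured from screening, neither threshold binds for patients entered at MMS 5–9 (step 4).
- **The reach is limited.** Both rules start when the primary endpoint is measured, and no effect on that endpoint was identified. Roll-over at Week 16 does not depend on response, so the rules affect it only through earlier exit.

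None of this removes the differences in number of occasions, reference visit and start time.

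**Conclusion.** The concern holds in this form: the protocol carries two worsening rules that give different exit times and can give different obligations, and no text ranks them. A patient who meets the 3.1.1 criteria once must leave under that section and has not yet met the worsening criterion in 7.2. The SAP adds doubt about whether the Day 57 assessment counts.

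The ceiling is a matter of arithmetic for the 3.1.1 rule at screening pMMS 5 or 6, and is conditional on a screening reference for the 7.2 rule. The MMS ≥ 4 condition does no work for any patient who could have been enrolled.

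The size in patients cannot be given. The documents report neither the distribution of screening pMMS nor how often a 2-point rise fails to persist. The consequences lie in consistency of patient management, Week 16 data and roll-over. The conclusion rests on the published scale and entry criteria and on reading the texts as written. It takes no view on which rule is clinically right.

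**What to change.** Reconcile the two synopsis entries, Protocol 3.1.1 and 7.2, and SAP 3.1 into one definition, used word for word in each place. It should state the reference visit, the score and threshold, the number of occasions and their spacing, whether Day 57 counts, and whether exit is mandatory or discretionary, in line with 7.1. It should also say how it applies to a patient whose reference pMMS leaves no room for a 2-point rise, and drop or justify any condition that cannot bind. If a repeat assessment is kept, the flow chart should show where it is obtained. Which rule to adopt is for the sponsor and investigators.

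The cost is amendment wording, a matching SAP edit and a notice to sites. Sample size and the primary analysis are unaffected.

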7.3. Study Discontinuation

All patients (Except those transitioning to the ABX464-104 study), regardless of the completion or premature discontinuation, should perform the End of Study Visit according to the study flow-chart.

7.4. Screen and Baseline Failures

A patient is considered to be a baseline failure if the patient signs the informed consent but withdraws before the baseline visit. All potential patients who are screened for enrolment in this study will be listed on the patient Screening Log/Identification List. Reasons for exclusion will be recorded for potential patients who do not enter the study.

A patient who does not fulfil the randomization criteria will be considered as a screen failure. All patient data should be entered in the eCRF including the screen failure data.

Based on the investigator evaluation and sponsor prior approval, a non-randomized patient can be re-screened. This re-screening procedure should be documented, the patient should consent again and a new unique and incremental patient Identification (ID) number be allocated.

8. ADVERSE EVENTS (AE) AND SERIOUS ADVERSE EVENTS (SAE)

The investigator is responsible for the detection and documentation of events meeting the criteria and definition of an AE or SAE. During the study, in case of a safety evaluation, the investigator or site staff will be responsible for reporting AEs and SAEs, as detailed in this section of the protocol.

During the screening period, all adverse events will be collected.

Any disease progression will be reported in the eCRF both as an adverse event and documented in the efficacy section.

8.1. Definitions

8.1.1. Definition of an AE

Any untoward medical occurrence in a patient or clinical investigation patient administered a pharmaceutical product and which does not necessarily have to have a causal relationship with this treatment.

An AE can therefore be any unfavorable and unintended sign (including an abnormal laboratory finding), symptom, or disease (new or exacerbated) temporally associated with the use of a medicinal product, whether or not considered related to the medicinal product.

Note: The official definition also extends to AEs occurring in the placebo arm. Because of regulatory requirements, events occurring during pre-and post-treatment periods will also be designated as AEs. Therefore, reporting of such events, AEs and SAEs, will commence when the patient is enrolled into the study (date of signature of the informed consent) up until 4 Weeks after the end of the treatment visits. The period after discontinuing study drug may be extended if there is a strong suspicion that the drug has not yet been eliminated.

8.1.2. Adverse Drug Reactions (ADR)

A response to a medicinal product which is noxious and unintended. Suggesting that there is at least a reasonable possibility or suspicion of a causal relationship between the medicinal product and an adverse event.

8.1.3. Definition of a SAE or Serious Adverse Drug Reaction (SADR)

A serious adverse event (experience) or reaction is any untoward medical occurrence that, at any dose:

- a) Results in death

NOTE: Death is an outcome of an AE, and not an AE in itself. Event which led to death should be recorded with fatal outcome.

- b) Is life-threatening

NOTE: The term 'life-threatening' in the definition of 'serious' refers to an event in which the patient was at risk of death at the time of the event. It does not refer to an event, which hypothetically might have caused death, if it were more severe.

- c) Requires hospitalization or prolongation of existing hospitalization

NOTE: In general, hospitalization means that the patient has been detained at the hospital or emergency ward for observation and/or treatment that would not have been appropriate in the physician's office or out-patient setting. Complications that occur during hospitalization are AEs. If a complication prolongs hospitalization or fulfills any other serious criteria, the event is serious. When in doubt as to whether "hospitalization" occurred, or was necessary, the AE should be considered serious.

Hospitalization for elective treatment of a pre-existing condition that did not worsen after informed consent was given is not considered serious.

- d) Results in persistent or significant disability/incapacity,

NOTE: The term disability means a substantial disruption of a person's ability to conduct normal life functions. This definition is not intended to include experiences of relatively minor medical significance such as uncomplicated headache, nausea, vomiting, diarrhea, influenza, and accidental trauma (e.g. sprained ankle) which may interfere or prevent everyday life functions but do not constitute a substantial disruption.

- e) Is a congenital anomaly/birth defect
- f) Is another medically important condition: This refers to an AE that may not be immediately life-threatening or results in death or hospitalization but may jeopardize the patient or may require intervention to prevent one of the outcomes listed above. Based on medical and scientific judgment this should usually be considered serious.

If there is any doubt about whether or not an AE is serious, the investigator should contact the sponsor.

8.2. A Suspected Unexpected Serious Adverse Reaction (SUSAR)

A Suspected Unexpected Serious Adverse Reaction (SUSAR), is a serious adverse reaction (SAR) for which a reasonable causal relationship with the medicine use is suspected but not confirmed. Unexpected in this context means not consistent with the applicable product information (e.g. investigator's brochure for an unapproved investigational product or Summary of Product Characteristics (SmPC) for an authorized product).

8.3. Events and/or Outcomes Not Qualifying as SAEs

Any hospitalization, or prolongation of hospitalization due to the circumstances listed below, will not be reported as SAE:

- planned medical/surgical procedure;
- planned medical/surgical admission (planned prior to entry into study, appropriate documentation required), for the disease under study;
- Administrative or social reasons (e.g. lack of housing, economic inadequacy, care-giver respite, family circumstances).

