1.1.2. Management of patients

Patients may live with a considerable symptom burden despite medical treatment (66% describe interference with work and 73% with leisure activities) [1] in the hope that the etiology of ulcerative colitis will be elucidated and a cure developed.

Although most patients present with mild-to-moderate UC, 10% of patients initially present with severe disease. Additionally, approximately 15% of patients will develop a severe flare during the course of their lifetime. Both the American College of Gastroenterology practice guidelines and the European Crohn's and Colitis Organization position statements define severe colitis as the passage of six or more stools per day with evidence of systemic toxicity (e.g., fever, tachycardia, anemia or elevated ESR) [2,3].

Patients with acute severe UC require hospitalization for optimal management owing to the seriousness of their illness. Although rates of death in severe UC have dropped by up to 25% with the adoption of more aggressive monitoring and treatment [4] acute severe colitis is still associated with a measurable mortality [5].

The use of intravenous steroids and improved surgical techniques probably explain much of the reduction in mortality associated with acute severe UC observed in the decades since their introduction [6].

Severe UC should be considered a medical emergency, and patients require close monitoring of stool frequency and vitals symptoms. Serial abdominal examinations and plain radiographs should be performed.

The cornerstone of management of severe UC remains the use of intravenous corticosteroids, which are effective in the induction of remission in the majority of cases. While many patients with acute severe ulcerative colitis will respond to a short course of intravenous corticosteroids, up to a third will fail to improve. In these patients with steroid-refractory colitis, the choice is between rescue medical therapy with cyclosporin, anti-TNF Alpha, vedolizumab, JAK inhibitors or surgery. Anti-tumor necrosis factor (TNF) therapy is effective for the treatment of ulcerative colitis (UC).

Nevertheless, up to 30% of patients show no clinical benefit despite optimal treatment, while another 40% of patients lose response over time and need to escalate or discontinue anti-TNF therapy within one year of treatment.

Thus, there is an unmet medical need for novel treatment options for patients with moderate to severe UC.

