3.1.3. Data Safety Monitoring Board

An independent Data Safety Monitoring Board (DSMB), with expertise and experience in the pathology, and without direct involvement in the conduct of the trial, will be set up specifically to guarantee effective protection of patients, to ensure the ethical conduct of the trial, to evaluate the benefit/risk ratio of the trial, and to ensure the independent review of the scientific results during the trial and at the end of the trial. Besides, the DSMB may recommend the early termination of the trial at any time if an unacceptable toxicity occurs. The DSMB will meet every 2 months.

The DSMB will oversee the adequate balance of baseline characteristics (gender, disease duration, concomitant treatment with corticosteroids, fecal calprotectin level, tobacco use) among the treatment groups.

In addition, DSMB will be review all potential causally-related Serious Adverse Events within 7 days of the initial report.

The DSMB has only a consultative role. It will inform the Sponsor who will decide whether the DSMB recommendation will be followed. A DSMB charter must be available upon submission of the trial (initial protocol) to the respective competent authorities.

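### The first bullet of Protocol 8.3 exempts admissions for any planned procedure from SAE reporting, with no pre-entry or no-worsening condition, which conflicts with 8.1.3(c)

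*Protocol*

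**What the plan says.** Protocol 8.1.3, criterion (c), makes an event serious if it "Requires hospitalization or prolongation of existing hospitalization". It allows one exception: "Hospitalization for elective treatment of a pre-existing condition that did not worsen after informed consent was given is not considered serious".

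Protocol 8.3 then removes some admissions from reporting: "Any hospitalization, or prolongation of hospitalization due to the circumstances listed below, will not be reported as SAE". Three circumstances follow:

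- Bullet 1: "planned medical/surgical procedure". Nothing is said about when it was planned, for which condition, or whether that condition had changed.
- Bullet 2: "planned medical/surgical admission (planned prior to entry into study, appropriate documentation required), for the disease under study".
- Bullet 3: administrative or social reasons, which is not at issue here.

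Three other places bear on the point. The opening text of Protocol section 8 requires disease progression to be recorded as an adverse event. Protocol 4.2.2 excludes, at screening, patients with a past or impending colectomy and those with bowel surgery that is recent or already planned. SAP 17.1.2 builds the SAE summaries from events marked serious on the adverse event page of the eCRF.

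**The concern.** A site that applies bullet 1 as it stands would not report, as an SAE, the admission of a patient whose UC worsens in the trial and who is then booked for surgery. This is a realistic route for this population. Protocol 1.1.2 describes the choice in steroid-refractory colitis as "rescue medical therapy with cyclosporin, anti-TNF Alpha, vedolizumab, JAK inhibitors or surgery", and patients who failed corticosteroids are eligible. Under Protocol 7.2 a treatment failure may be withdrawn and moved to standard of care. Under 8.5, AEs and SAEs are collected until 4 weeks after treatment stops, so surgery booked soon after failure can fall inside the collection period.

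Three things depend on the serious flag: 24-hour reporting (Protocol 8.5 and 8.7), the SAE tables (SAP 17.1.2), and the commitment that the DSMB will "review all potential causally-related Serious Adverse Events within 7 days of the initial report". The incidence of treatment-emergent SAEs by arm is also a listed secondary endpoint (Protocol 2.4). If sites read 8.3 differently, like events will be classified differently. If worsening of UC differs between arms, the under-recording could differ too.

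**Working it through.** No calculation decides this point. The check is to run the relevant kinds of admission through both sections.

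| Admission | 8.1.3(c) | 8.3 bullet 1, read literally | 8.3 bullet 2 | Result |
|---|---|---|---|---|
| A. Procedure planned before consent, condition unchanged | Not serious | Exempt | Exempt if for UC and documented | Agree |
| B. Procedure planned after consent because UC worsened | Serious | Exempt | Not exempt (not planned before entry) | **Conflict** |
| C. Admission for worsened UC, scheduled after entry, no procedure | Serious | Does not apply | Not exempt | Agree: reportable |
| D. Unplanned admission for worsened UC | Serious | Does not apply | Does not apply | Agree: reportable |

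1. *Is there a missing condition?* Yes. Bullet 2 has a pre-entry condition and 8.1.3(c) has a no-worsening condition. Bullet 1 has neither.

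2. *Does it matter for bowel surgery?* Yes. Because 4.2.2 excludes patients with surgery already planned or colectomy impending at screening, a colectomy in an eligible patient will almost always have been planned after entry. For bowel surgery, bullet 1 therefore has hardly any row A cases to cover and mainly catches row B.

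3. *Is the underlying event subject to the seriousness criteria?* Yes. Disease progression is an AE under the opening text of section 8, so criterion (c) applies to an admission that results from it.

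4. *What is lost in row B?* The serious flag as far as it rests on hospitalization. The event itself stays in the data: progression is recorded as an AE, and SAP section 11 says that conditions or procedures arising after screening are recorded as adverse events. The event can still be counted in the tables of grade 3 or 4 TEAEs (Protocol 9.3) and of TEAEs leading to discontinuation of study drug or of the study (SAP 17.1.3 and 17.1.4).

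5. *Size.* One patient is 1/61 = 1.6 percentage points of a planned arm. That is only the unit of measurement. The documents give no rate of planned surgery or of procedure-related admission, so the number of events affected cannot be estimated.

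**The case against.** The best defence is that the specific bullet governs the general one. An inpatient colectomy is also a planned surgical admission for the disease under study, which bullet 2 addresses directly. On that reading bullet 1 covers only procedures for other conditions, the pre-entry limit holds for UC surgery, and 8.3 agrees with 8.1.3(c). The reading is sensible, but the protocol does not state it. The bullets are separate alternatives, and meeting any one is enough. The defence shows that sites could classify the event either way, which is itself a defect in a reporting rule.

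A second defence is that 8.1.3 has other safeguards. Worsening UC may be serious as life-threatening, disabling or medically important (criteria b, d and f), and the investigator is told to contact the sponsor when seriousness is in doubt. This stands in part. Criterion (f) depends on judgement, however, and a categorical exemption leaves a literal reader with no doubt to raise.

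Four stronger readings are tempting, and the documents do not support them.

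- *Any UC admission scheduled during the trial escapes.* Bullet 2 keeps such an admission reportable unless it is for a procedure (row C).
- *The colectomy is not an SAE, or disappears from the data.* Section 8.3 speaks only to the hospitalization. The worsening and the procedure remain AEs and may be serious on other criteria.
- *DSMB oversight is bypassed.* The 7-day review covers only potentially related SAEs, so an event judged unrelated would not have entered it anyway. The two-monthly safety review (Protocol 3.1.3, SAP 4.1) continues.
- *The loss can be sized from the 8 SAEs among 211 subjects in Protocol 1.2.5.2.* That count mixes healthy volunteers, HIV patients and UC patients, single and repeated dosing, and exposure approaching 2 years, and it counts events rather than subjects. It gives no expected count for 61 UC patients over 16 weeks, and still less for the placebo arm or for the few SAEs whose only criterion is a planned procedure.

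**Conclusion.** Bullet 1 of 8.3 is wrong as written. Read literally, it removes from SAE reporting an admission that 8.1.3(c) makes serious: one for a procedure scheduled during the trial because UC worsened. The two sections must be reconciled.

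The consequence is limited to the serious flag and what depends on it: 24-hour reporting, the SAE tables and, for potentially related events, the 7-day DSMB review. The primary endpoint and its analysis are not affected. The size is unknown. The conclusion assumes that at least some sites would apply bullet 1 on its own terms; the documents contain nothing to stop them. Whether any loss would differ by arm, and in which direction, cannot be told from the documents.

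**What to change.** Amend bullet 1 of 8.3 so that it covers only a medical or surgical procedure planned before informed consent, for a condition that has not worsened since consent, with documentation. Consent is the natural reference date, because 8.1.3 uses it and AE collection starts there under 8.5. Add a sentence that admissions for procedures scheduled after consent, including for UC, are assessed under 8.1.3. Put the same wording in the SAE completion guidance.

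For patients already treated, query procedure and hospitalization records for admissions exempted under bullet 1, and reassess each against 8.1.3 without knowledge of treatment.

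The cost is one line of protocol text, a guidance note, a targeted query and a few more SAE reports. The change does not make every later procedure serious: elective treatment of an unchanged pre-existing condition is still released by the exception in 8.1.3(c).
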